## 1.2. Rationale

Tenofovir disoproxil fumarate (TDF), the oral pro-drug of tenofovir (TFV), is a nucleotide analogue that inhibits viral polymerases by direct binding and after incorporation into DNA, by termination of the DNA chain [Heijtink, 1994]. TDF is a highly potent treatment in treatment-naïve and LAM resistant CHB patients [Baran, 2013]. In vitro studies have shown that HBV strains expressing the ADV resistance-associated substitutions rtA181V and/or rtN236T showed reductions in susceptibility to TDF ranging from 2.9-fold to 10-fold that of wild-type virus[Brunelle, 2005; Villet, 2008], but clinical trials[Berg, 2010] showed TDF mono-therapy resulted in complete viral suppression in the majority of patients with partial response to ADV by week 48, suggesting that this drug may be an effective treatment for patients who have previously failed treatment with different NAs.

Until recently, data on the efficacy of TDF treatment following failure of multiple NAs were limited. Patterson and colleagues reported the results of a prospectively conducted study that evaluated TDF treatment in CHB patients who had previously failed with LAM and followed by at least 24 weeks of ADV treatment. Serum HBV DNA at study entry were  $>10^5$  copies/ml and  $>10^4$  copies/ml in HBeAg-positive (n=40) and HBeAg negative patients (n=20), respectively. Those receiving combination ADV and LAM were switched to TDF plus LAM, and those on ADV monotherapy were switched to TDF monotherapy. At week 48 and 96, 27/59 (46%) and 38/59 (64%) patients achieved a HBV DNA <15 IU/mL. HBV DNA response was independent of baseline LAM therapy or mutations conferring ADV resistance. In another study, van Bommel and colleagues also investigated efficacy of TDF in patients with prior failure or resistance to different NAs. Of the 131 eligible patients in this retrospective study, 121 patients (93%) were LAM-experienced and 110 (85%) were ADV-experienced. Most patients had previously received sequential therapy with LAM and ADV (56%) or combination therapy with LAM and ADV (22%) after HBV DNA breakthrough during monotherapy. Three patients showed no response to ETV treatment. Resistance analysis in 113 of the 131 patients revealed genotypic LAM and ADV resistance in 62% and 19% of patients, respectively. The overall cumulative proportion of patients achieving HBV DNA levels <400 copies/ml was 79% after a mean treatment duration of 23 months. Although LAM

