### 5.1.2. Dosage and Administration

Subjects will be assigned to receive Tenofovir disoproxil fumarate (TDF) 300 mg once daily during the study period.

Subjects will be instructed to return unused study medication in the original container at each post-baseline study visit. The Investigator will be responsible for maintaining accurate records for all study drug and study drug bottles dispensed and returned. The inventory must be available for inspection by the study monitor. Study medication

supplies, including partially used or empty bottles, must be accounted for and the dispensing logs must be verified by the study monitor prior to destruction or return.

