5.3 Exploratory endpoints

- Evaluate the impact of the baseline host and virological characteristics (HBV DNA level, resistance type, HBeAg status, prior treatment with ADV, prior treatment with ETV, prior treatment with IFN, overall duration of prior NA treatment, compliance, cirrhosis, ALT level, age, gender, BMI, AST, r-GT, platelets, INR, total bilirubin, albumin, etc.) and early HBV DNA suppression on response to TDF at week 144.
- Time to virological response to TDF (defined as HBV DNA <20 IU/mL) for overall and subjects with different patterns of mutation.

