7. STATISTICAL ANALYSIS

7.1 Subject screening, disposition and protocol deviations

The screening failure subjects and the reasons for screening failure will be summarized by the numbers and percentages. The percentages are based on the number of screening failure subjects.

The disposition of subjects will be summarized, including the numbers and percentages of subjects for the following categories: all enrolled subjects, subjects completed the study, subjects early discontinued from the study, subjects in the modified intent to treat population, subjects in the perprotocol population, and subjects in the safety analysis population. All percentages are based on the number of all enrolled subjects.

The primary reason for subject premature discontinuation from study will also be summarized. The reasons for discontinuation will include voluntarily discontinue participation, lost to follow-up, lack of efficacy, subjects with treatment interruptions of ≥ 28 consecutive days, adverse event, intercurrent illness, protocol violations, pregnancy, and other reason. A listing will be provided.

Protocol deviations will be summarized and listed for mITT population. Subject counts and percentages will be displayed by the following deviation categories:

- Poor compliance, defined as taking < 80% or > 120% of the required number of tablets
- Take the prohibited medication specified in protocol during the treatment period
- With actual visit day being more than 14 days deviated from the schedule visit day
- · Had other significant protocol violations that were thought to affect the efficacy evaluation

Major protocol deviations which results in the exclusion of the subject from PP population will be discussed, determined, and documented by study team before final database lock.

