7.3.3 Treatment compliance

The duration in days of study drug exposure from first dose date to the last dose date will be summarized by descriptive statistics.

The duration of the drug exposure (day) = Last dose date - First dose date + 1

Treatment compliance, defined as actual taken amount divided by expected taken amount per protocol times 100, will be summarized by descriptive statistics for mITT. The formulas for calculating the treatment compliance are as follows:

Treatment Compliance (%) = Actual taken amount×100 / Expected taken amount

Drug accountability information including date (dispensed or returned), dispensed amount, returned amount, lost amount, expected taken amount, actual taken amount, missing amount, and treatment compliance will be presented in the listing.

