7.4.2 Analysis of secondary variables

Analysis for secondary variable of the log₁₀ reduction in serum HBV DNA by patterns of mutation and overall per visit will be summarized by descriptive statistics as the mean, standard deviation, two-sided 95%CI, minimum, median, maximum, and the number of observations. The patterns of mutation will be summarized by 2 categories. One includes wild-type, LAM-R, ADV-R and ETV-R. The other one includes wild-type, ADV-R single mutation (A181T/V; N236T), ADV-R double mutation (A181T/V+N236T)) and other mutation. Nominal P values between different patterns of mutation will be provided at week 24, 48, 96, 144. Individual HBV DNA levels of subjects with genotypic resistance to ADV (A181T/V+N236T) will be summarized over time by figure.

In addition, the number and percentage will be presented respectively for secondary variables including:

- The proportion of subjects with virological response (serum HBV DNA <20 IU/mL and serum HBV DNA <69 IU/mL, separately) by visit
- The proportion of subjects with virological response (serum HBV DNA <20 IU/mL and serum HBV DNA <69 IU/mL, separately) by visit in the subgroup with confirmed multi-drug resistance at baseline
- The proportion of subjects with virological response(serum HBV DNA <20 IU/mL and serum HBV DNA <69 IU/mL, separately) by visit in the subgroup with medical history (previously exposed to ADV >6 months or not, ETV >6 months or not) (Subjects with ETV >6 months will be separated as ETV-R and non ETV-R)
- The proportion of subjects achieving HBeAg loss, HBeAg seroconversion, HBsAg loss and

HBsAg seroconversion at Week 48, 96 and 144 for HBeAg positive subjects

- The proportion of subjects achieving HBsAg loss and HBsAg seroconversion at Week 48, 96 and 144 for HBeAg negative subjects
- The proportion of subjects with ALT normalization at week 48, 96 and 144 in subjects who have abnormal ALT at baseline
- The incidence of subjects who experience viral breakthrough (defined as 1 log increase in HBV DNA from nadir determined by two sequential HBV DNA measurements) overall and by each visit.
- The proportion of subject with unsatisfactory response, overall and by each visit. Unsatisfactory response is defined as subjects who have HBV DNA ≥200 IU/mL at week 48 and afterwards have ≤1 log10 IU/mL decrease in HBV DNA at two consecutive tests, confirmed by a third visit (additional visit) at least one month apart
- Mutation pattern change from baseline at week 48, 96, 144

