7.4.3 Exploratory analysis

The exploratory analysis is to evaluate the impact of the baseline host and virological characteristics (viral titer, mutation patterns, etc.) and early HBV DNA suppression on response to TDF at week 144. Multiple-factor logistic regression analysis will be used to assess the baseline variables that were significantly associated with HBV DNA negativity at week 144. The factors includeHBV DNA level, resistance type, HBeAg status, prior treatment with ADV, prior treatment with ETV, overall duration of prior NA treatment, compliance, cirrhosis, ALT level, age, gender, BMI, AST, r-GT, platelets, INR, total bilirubin, albumin, etc. The OR and 95% CI of each factor will be provided in the table.

Time to virological response to TDF defined as HBV DNA <20 IU/mL, as a time-to-event variable, will be analyzed by Kaplan-Meier curve for overall and subjects with different patterns of mutation. Log-rank test will be performed separately for each of the following factors: HBV DNA level, HBeAg status, prior treatment with ADV, resistance type (ADV or not), cirrhosis, compliance and

patterns of mutation. Cox regression model will be conducted to include all above factors and additional factors: prior treatment with IFN, ALT level, age, and gender.

In addition, three listings will be provided for

- The ALT for patients with any HBeAg Loss, HBeAg Seroconversion, HBsAg Loss and HBsAg Seroconversion over time
- The relationship between HBV DNA and medical history for previously exposed to NAs >6 months
- The HBV DNA for patients with virological breakthrough (defined as 1 log increase in HBV DNA from nadir determined by two sequential HBV DNA measurements), and
- The HBV DNA for patients with unsatisfactory response (defined as subjects who have HBV DNA ≥200 IU/mL at week 48 and afterwards have ≤ 1 log10 IU/mL decrease in HBV DNA at two consecutive tests, confirmed by a third visit (additional visit) at least one month apart).

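### The Cox model in SAP 7.4.3 holds two overlapping ADV-resistance factors, exactly redundant under the most direct codings, and treats compliance as fixed although its value can include tablets taken after response

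*SAP*

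**What the plan says.** SAP 7.4.3 plans Kaplan-Meier curves for time to first HBV DNA <20 IU/mL and a separate log-rank test for each of seven factors. The list contains "resistance type (ADV or not), cirrhosis, compliance and" and ends with the patterns of mutation. One Cox model follows: "Cox regression model will be conducted to include all above factors and additional factors: prior treatment with IFN, ALT level, age, and gender". The results go to Tables 4.12.1 (mITT) and 4.12.2 (PP).

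SAP 7.4.2 defines two codings of mutation pattern. The first (Category 1) has the levels wild-type, LAM-R, ADV-R and ETV-R. For the second (Category 2): "The other one includes wild-type, ADV-R single mutation (A181T/V; N236T), ADV-R double mutation", with other mutation as the fourth level. Section 7.4.3 does not say which coding enters the Cox model, or where a subject with resistance to more than one drug is placed.

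On compliance, SAP 7.3.3 says: "Treatment compliance, defined as actual taken amount divided by expected taken amount per protocol times 100". It gives no time window, and the exposure period defined beside it runs from first to last dose. The only cut-point in the SAP is a protocol-deviation rule in section 7.1: "Poor compliance, defined as taking < 80% or > 120% of the required number of tablets". SAP 5.3 lists compliance among baseline characteristics: "prior treatment with IFN, overall duration of prior NA treatment, compliance, cirrhosis, ALT level".

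**The concern.** Two factors that carry the same information cannot both have their own coefficient. If ADV yes/no is a sum of pattern terms, the software drops one column, and the hazard ratio labelled ADV changes meaning with the column dropped. The effect of ADV resistance on response to TDF is a question that Protocol 1.2 calls unsettled, and the impact of mutation patterns is part of a secondary objective (Protocol 2.2, SAP 2.2).

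Compliance is a different problem. A subject who responds at week 48 goes on taking tablets to week 144. If compliance is computed over the whole treatment period and used as a fixed covariate, part of it is measured after the event it is meant to predict. A hazard ratio for compliance could then reflect behaviour after response.

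**Working it through.** Section 7.4.3 gives no figure to reproduce. The trial size used below is the plan's own: 0.80 × 0.20 × (1.96/0.06)² = 170.7 (stated 170), and 170/0.85 = 200.

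**ADV terms, Category 2.** Take wild-type as reference, with indicators S (single), D (double) and O (other). If every ADV-resistant subject is in S or D, then ADV = S + D. The columns ADV, S, D, O number four and have rank 3. This is algebra and needs no assumption about frequencies.

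Consequence, with illustrative true hazard ratios against wild-type of 0.7 (single) and 0.4 (double):

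| Column dropped | ADV term | Remaining ADV-pattern term |
|---|---|---|
| Single | 0.7 | double: 0.4/0.7 = 0.57 |
| Double | 0.4 | single: 0.7/0.4 = 1.75 |
| ADV | none | single 0.7, double 0.4 |

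Cox fits to 20,000 simulated subjects gave 0.71 with 0.56, 0.40 with 1.78, and 0.71 with 0.40. The hazard ratio for other mutation was 1.01 in all three.

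**ADV terms, Category 1.** If all ADV-resistant subjects are in the ADV-R level, ADV equals that level, and the rank is again 3 of 4. If some are placed elsewhere, the rank is 4. The variance inflation factor (VIF) for ADV then depends on the share m of subjects in levels that mix ADV-resistant with other subjects. If ADV resistance is independent of those levels, VIF = 1/m. Assume LAM-R in 60% of subjects (a cited cohort in Protocol 1.2 had 62%) and ETV-R in 20% or 30% of these.

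- ETV-R first, then ADV-R: m = 0.6 × 0.2 = 0.12 or 0.6 × 0.3 = 0.18, so VIF = 8.3 or 5.6. Simulated medians at n = 200 were 5.7 to 8.7, which makes the ADV standard error √5.7 = 2.4 to √8.7 = 2.9 times larger.
- LAM-R ahead of ADV-R: m = 0.6, VIF = 1.7. The collinearity is modest, but the ADV-R level then holds only subjects without LAM resistance.

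**Compliance: time after response.** (144 − 24)/144 = 83% of the period follows a week-24 response, and (144 − 48)/144 = 67% a week-48 response. Protocol 1.2 reports for a cited prospective study: "At week 48 and 96, 27/59 (46%) and 38/59 (64%) patients achieved a HBV DNA <15 IU/mL". With those rates and the planned 80% at week 144, about 59% to 60% of responders' treatment time lies after the event. These shares measure exposure to the problem; they do not measure bias.

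**Compliance: illustration of bias.** Simulated trials of 200 subjects, visits every 12 weeks, the response curve above, and adherence unrelated to response until it occurs. Log-rank rejection at a nominal 5%, by whole-treatment compliance group:

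| Assumed mean adherence, cut | No change after response | 2-point fall after response |
|---|---|---|
| 88%, cut 80% | nominal (about 5%) | 14% to 15% |
| 95%, cut 80% | nominal or lower | 4% |
| 95%, cut 95% | about 6% | 32% and 50% in two simulations |

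Mean, spread, cut and shift are all assumptions. In the simulations with mean adherence 88% or 91%, compliance to date as a time-dependent term rejected in 4% to 6% of trials in every scenario, including 5-point shifts.

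**The case against.** The analysis is exploratory, no hypothesis is tested (Protocol 8.1), and Kaplan-Meier curves by both mutation schemes are planned whatever happens in the Cox model (Figures 4.10.1.1 to 4.10.2.2). An exact redundancy would show up at programming. The mock tables are in a separate document and may settle the coding. For compliance, the size is unknown. Inclusion criterion 6 requires that the physician judged the subject adherent to earlier therapy, so compliance may be high and stable, and an 80% split would then leave almost nobody in the low group.

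All of this stands, and it limits the weight of the point. It does not remove it. The SAP text lists both ADV factors for one model, and noticing the redundancy at programming would leave the choice of ADV term to be made after the data are in hand.

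Four stronger readings are tempting and are not supported:

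- *That the ADV hazard ratios are uninterpretable under any coding.* Some Category 1 orderings give full rank, and the SAP does not say which coding applies. Exactness under Category 2 also requires that ADV yes/no use the same substitutions. Protocol 1.3.2 counts rtA181S as ADV-associated, whereas the SAP's single-mutation level names only A181T/V and N236T.
- *That the whole Cox model fails.* The other coefficients and an ADV contrast remain estimable.
- *That the compliance comparison is known to be biased.* With no change in adherence after response, the test keeps its level, and nothing in the documents shows that adherence changes.
- *That the long factor list makes the week-144 logistic model unreliable.* In simulation with 18 terms, coverage was 93% to 94% and false positives 6% per null factor. Penalising that model would be a preference.

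**Conclusion.** The point holds in conditional form. Under Category 2 with matching definitions, or Category 1 with all ADV-resistant subjects in the ADV-R level, the separate ADV hazard ratios are arbitrary. That conclusion rests on algebra. With ETV-R placed first and ADV-R next they are estimable but imprecise (standard error 2.4 to 2.9 times larger under the assumed resistance frequencies). With LAM-R ahead of ADV-R the inflation is small.

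The compliance factor is wrongly specified, because a fixed covariate can contain data from after the event. Whether this distorts the result depends on a change in adherence after response that the documents do not quantify. The simulated rates, from 4% to 50% for the same 2-point fall, show only how strongly the size depends on assumptions. In SAP 5.3, calling compliance a baseline characteristic is a labelling error.

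The primary estimate, its confidence interval and the sample size are not affected.

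**What to change.** In SAP 7.4.3:

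1. Enter one mutation-pattern factor in the Cox model. State which coding it uses, make the levels mutually exclusive, and give a precedence rule for subjects resistant to more than one drug.
2. Drop ADV yes/no from the Cox model and report the ADV effect as a contrast of the pattern levels. Its separate log-rank test can stay.
3. Remove compliance from the log-rank tests. In the Cox model, use cumulative compliance to date as a time-dependent covariate, or omit it. The data exist, since Protocol 5.1.2 says: "Subjects will be instructed to return unused study medication in the original container at each post-baseline study visit". Cutting compliance at each subject's own response is a weaker remedy, because the window length then depends on the event. In one simulated setting (90% cut, 10-point fall) it still rejected in 11% of trials, with a hazard ratio of 0.87.

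In SAP 5.3, remove compliance from the list of baseline characteristics.

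Cost: SAP wording and minor programming on data already collected. One fewer ADV hazard ratio and one fewer log-rank test are reported.

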In the last two decades, revolutionary changes happened in the management of chronic hepatitis B virus (HBV) infection. Nucleos(t)ide analogues (NAs) target the reverse transcriptase of hepatitis B virus (HBV), and are potent inhibitors of viral replication. In China lamivudine (LAM) was approved for the treatment of chronic hepatitis B in 1999. Subsequently, adefovir (ADV) and entecavir (ETV) were launched at 2005 in China. Then telbivudine (LdT) was licensed by CFDA (China Food and Drug Administration) in 2008. According to the international guidelines [European Association For The Study Of The Liver, 2012; Liaw, 2012; Lok, 2009], ETV and TDF should be considered for initial therapy for naïve patients because of superior viral suppression low risk of resistance development. But in a resource-limited country such as China, LAM, ADV and LdT remain widely used. The major problem with LAM is the high incidence of resistance, with up to 70% of patients developing drug related mutations after 4 years of treatment [Lai, 2003]. This makes it unsuitable for use as the first line oral antiviral drug in most circumstances. But in China LAM is still accepted as a first line antiviral agent because of its relatively low daily cost and well-established safety profile. Thus, the number of LAM resistant patients is high and management of LAM resistance is becoming a challenge for Chinese physicians.

The treatment options for patients who develop LAM resistance have been limited. ETV is potent and proven to have a high genetic barrier to resistance in NA-naïve HBV patients. After five years of ETV mono-therapy, only 1.2% of treatment naïve patients developed genotypic resistance to ETV [Tenney, 2009]. However, ETV was less potent and the frequency of resistance was increased in LAM refractory chronic HBV patients [Sherman, 2008; Sherman, 2006]. After five years of treatment, 51% of LAM-refractory patients showed genotypic ETV-resistance and in 43% a virological breakthrough was also observed [Tenney, 2009]. Another option for LAM resistant patients is LAM plus ADV combination therapy. This approach can reduce the risk of multi-drug resistance,

but the HBV DNA suppression may not be adequate. Recent studies from Asia demonstrated that only 22.6% to 41.3% [Chung, 2011; Ryu, 2010; Sheng, 2011; Son, 2012] of LAM resistant patients achieved HBV DNA undetectable after 48 weeks of ADV+LAM treatment.

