## 4.2. Inclusion Criteria

Specific information regarding warnings, precautions, contraindications, adverse events, and other pertinent information on the GSK investigational product or other study treatment that may impact subject eligibility is provided in the IB/IB supplement(s).

Deviations from inclusion criteria are not allowed because they can potentially jeopardise the scientific integrity of the study, regulatory acceptability or subject safety. Therefore, adherence to the criteria as specified in the protocol is essential. Subjects eligible for enrolment in the study must meet all of the following criterion:

- 1. Aged between 18–65 years (inclusive).
- 2. Male or female; a female is eligible to enter and participate in this study if she is of:
  - a. Non-childbearing potential (i.e., physiologically incapable of becoming pregnant, including any female who is post-menopausal); or,
  - b. Child-bearing potential, has a negative urine pregnancy test at baseline, and agrees to one of the following methods for avoidance of pregnancy during the period of the study and until 30 days after last dose of study medication:
    - Oral contraceptive, either combined or progestogen alone.
    - Injectable progestogen.
    - Implants of levonorgestrel.
    - Oestrogenic vaginal ring.
    - Percutaneous contraceptive patches.
    - Intrauterine device (IUD) or intrauterine system (IUS) showing that the expected failure rate is less than 1% per year as stated in the IUD or IUS product label.
    - Has a male partner who is sterilised.
    - Double barrier method: condom and an occlusive cap (diaphragm or cervical/vault caps) with a vaginal spermicidal agent (foam/gel/film /cream/suppository).
- 3. The ability to understand and sign a written informed consent prior to any studyrelated procedure and comply with the requirements of the study.
- 4. Positive HBsAg for more than 6 months, and anti-HBs negative.
- 5. Serum HBV DNA level  $\geq 200$  IU/ml at study screening (Use central lab results).
- 6. Experienced multiple NAs treatment failure which is defined as HBV DNA higher than 200 IU/ml after two or more different NA(s) treatments (i.e. initiate with mono-therapy, followed by add-on/switch rescue therapy; at least 6 months continuous treatment for each regimen, total duration to be no less than 12 months). In addition, subjects judged by the treating physician to have adhered to previous NA therapy.

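### The exploratory Cox model for time to virological response includes prior ADV but omits prior ETV without a stated reason, so its ADV hazard ratio may be confounded

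*SAP*

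**What the plan says.** SAP 7.4.3 plans two multivariable models.

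- **Logistic model for week-144 response.** Its list contains "prior treatment with ADV, prior treatment with ETV, overall duration of prior NA treatment", along with host, viral and laboratory factors.
- **Time to response.** Separate log-rank tests are planned for "HBV DNA level, HBeAg status, prior treatment with ADV, resistance type (ADV or not), cirrhosis, compliance and" patterns of mutation. Then: "Cox regression model will be conducted to include all above factors and additional factors: prior treatment with IFN, ALT level, age, and gender".

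Elsewhere in the SAP, prior ETV is a factor of interest. The exploratory endpoint in SAP 5.3 names "prior treatment with ADV, prior treatment with ETV, prior treatment with IFN", and SAP 7.4.2 reports response by visit in subgroups "previously exposed to ADV >6 months or not, ETV >6 months or not".

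Protocol 4.2, inclusion criterion 6, defines multiple treatment failure as "HBV DNA higher than 200 IU/ml after two or more different NA(s) treatments". Protocol 1.1 discusses ETV for lamivudine (LAM) resistant patients and then adds: "Another option for LAM resistant patients is LAM plus ADV combination therapy".

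**The concern.** Prior ADV is in the Cox model and prior ETV is not. If the two exposures are associated in the enrolled population, and ETV history has its own influence on response to tenofovir (TDF), part of the ETV effect will be attributed to ADV. If ETV history slows response and is commoner among subjects without ADV, the ADV hazard ratio is pushed upward. A real ADV disadvantage would be diluted, or a null effect would look like an advantage.

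The Cox and logistic results for ADV will probably be read side by side. As planned, one is adjusted for ETV history and the other is not.

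**Working it through.** **1. Which factors the Cox model contains.** The factors above could in principle mean the logistic list. They cannot sensibly do so, because ALT, age and gender are called additional although the logistic list already has them. They therefore mean the log-rank list.

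| Factor | SAP 5.3 | Logistic | Log-rank | Cox |
|---|---|---|---|---|
| Prior ADV | yes | yes | yes | yes |
| Prior ETV | yes | yes | no | no |
| Duration of prior NA treatment | yes | yes | no | no |
| Prior IFN | yes | no | no | yes |

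**2. Whether entry links ADV and ETV.** SAP 7.2.2 tracks four prior NAs: LAM, telbivudine (LdT), ETV and ADV. Leave aside TDF taken more than 6 months before screening, which is allowed. A subject without ADV needs at least two of LAM, LdT and ETV, and two of those three pairs contain ETV. A subject with ADV needs only one more drug.

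Let l, d and e be the exposure rates for LAM, LdT and ETV before selection. Assume the exposures are independent; this and the rates are assumptions, since the documents give none.

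- P(ETV | ADV) = e / [1 − (1−l)(1−d)(1−e)]
- P(ETV | no ADV) = e·k / [e·k + l·d·(1−e)], with k = 1 − (1−l)(1−d)

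With l = 0.70, d = 0.30, e = 0.35:

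- with ADV: 0.35 / (1 − 0.1365) = 41%
- without ADV: 0.2765 / (0.2765 + 0.1365) = 67%

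The odds ratio between the two exposures is l·d/k². It is below 1 unless l = d = 1, because k is at least as large as both l and d. Under independence, then, selection alone makes the association negative. Its size depends on the rates: with e = 0.35 it is 37% v 50% for l = d = 0.70, and 37% v 92% for l = 0.90, d = 0.05.

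**3. What omission does to the ADV hazard ratio.** Take a true ADV hazard ratio of 1.0 and an ETV hazard ratio h. With ETV omitted, the starting hazard ratio for ADV is

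[1 − (1−h)·P(ETV | ADV)] / [1 − (1−h)·P(ETV | no ADV)].

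| ETV with ADV v without | h = 1.0 | h = 0.8 | h = 0.6 |
|---|---|---|---|
| 37% v 50% | 1.00 | 1.03 | 1.06 |
| 41% v 67% | 1.00 | 1.06 | 1.14 |
| 37% v 92% | 1.00 | 1.13 | 1.34 |

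A simulation agrees in pattern (20,000 subjects per scenario, 12-weekly visits, 80% response by week 144 in the reference group, 60% prior ADV, no other covariates):

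| ETV with ADV v without | h = 1.0 | h = 0.8 | h = 0.6 |
|---|---|---|---|
| 50% v 50% | 0.99 | 1.00 | 0.98 |
| 40% v 60% | 1.00 | 1.05 | 1.13 |
| 20% v 80% | 1.00 | 1.15 | 1.36 |
| 10% v 90% | 1.01 | 1.24 | 1.52 |

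With ETV added, every estimate returns to 0.95-1.05, which is simulation noise. Without an association, or without an ETV effect, there is no bias.

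**4. Whether mutation patterns cover it.** SAP 7.4.2 defines two categorisations. "One includes wild-type, LAM-R, ADV-R and ETV-R"; the other has wild-type, single and double ADV mutations, and other mutation, so no ETV level. SAP 7.4.3 does not say which one enters the Cox model. The first records detected ETV resistance, not exposure, and SAP 7.4.2 itself separates ETV-exposed subjects into ETV-R and non ETV-R. If ETV acts only through resistance, present in half of those exposed, the unadjusted ADV hazard ratio at 20% v 80% is 1.06-1.10. Adjusting for ETV-R then removes the bias (0.96-0.99).

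**5. Precision.** The plan states no figure for the Cox model. Its 170 and 200 subjects concern the primary proportion: 0.8 × 0.2 × (1.96/0.06)² = 170.7, and 170/0.85 = 200. At 80% response, 200 subjects give about 160 events. If 70% had ADV, the standard error of the log ADV hazard ratio is about 1/√(160 × 0.7 × 0.3) = 0.17. Adding ETV multiplies it by 1/√(1−r²), where r is the ADV-ETV correlation:

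- ETV 35% v 70%: r² = 0.0735²/(0.21 × 0.248) = 0.104, factor 1.06
- ETV 35% v 90%: r² = 0.1155²/(0.21 × 0.250) = 0.254, factor 1.16

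Simulation with 200 subjects gives 0.174 rising to 0.185-0.203, that is 6-17%. Against a standard error of 0.174, a bias of 1.05-1.13 is 0.3-0.7 standard errors, and 1.36 is 1.8.

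**The case against.** The strongest reply is that what is certain here is only an unexplained difference between two exploratory covariate lists. Much of that reply stands.

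- **Alternative routes.** A reader might infer that criterion 6 makes ADV and ETV alternative rescue treatments. It names neither drug and allows a subject to have had both or neither, for example LAM then LdT. The contrast between the two options appears only in the background on LAM resistance. The selection argument survives without it, but heavily pretreated patients who cycled through every drug would weaken the association.
- **Proven confounding.** Bias needs both an ADV-ETV association and an ETV effect beyond the other covariates. The documents quantify neither. The calculations above leave out most of the planned Cox covariates, including ADV resistance type, HBeAg status and cirrhosis, so they show a possible range and not this trial's bias.
- **Relevance.** The question left open in Protocol 1.2 is how ADV resistance, not ADV exposure, affects response. Resistance has its own Cox term.
- **Disagreement between models.** A reader might attribute any difference between the Cox and logistic results to ETV adjustment. The models also differ in outcome and in several laboratory covariates.
- **Prior ETV is examined elsewhere**, in the logistic model and in the subgroups of Tables 4.4.1-4.4.2. Whether those tables could also mislead cannot be judged, because the mock tables are in a separate document.

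None of this explains why prior ETV is dropped from the Cox model when the SAP treats it as a candidate predictor in three other places.

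**Conclusion.** The omission is real and unexplained. The ADV hazard ratio from the Cox model may be confounded by ETV history; the documents do not support saying that it is. The direction is plausible, because requiring failure of at least two NAs tends to leave more ETV exposure among subjects without ADV. That tendency rests on assumed exposure rates and independence before selection.

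With a true ADV hazard ratio of 1.0 and an assumed ETV hazard ratio of 0.6-0.8, omission gives about 1.03-1.14 in the milder exposure scenarios and up to about 1.5 when exposures are almost exclusive. It gives about 1.0 if either condition fails. If ETV history speeded response, the bias would run the other way. The mutation-pattern term may absorb some of the effect, but cannot be relied on to do so.

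This is a small, well-defined correction to an exploratory analysis. No hypothesis is tested in the study, and the primary endpoint and sample size are untouched.

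**What to change.** In SAP 7.4.3:

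1. Add prior treatment with ETV to the log-rank factors and to the Cox model, defined in the same way as prior ADV.
2. Add overall duration of prior NA treatment to the Cox model, so that it agrees with SAP 5.3 on treatment history.
3. If the sponsor prefers to leave either factor out, state the reason before database lock.

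The cost is SAP wording and programming. Prior treatment by drug, including ETV, is already collected and summarised under SAP 7.2.2. About 160 expected events can carry one or two more terms. The statistical price is some precision: if ETV has no effect, the standard error of the log ADV hazard ratio rises by about 6-17% under the exposure rates assumed above. The cost of adding duration was not calculated.
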